#### Other

A sponsor shall, upon request by a reviewing IRB or FDA, provide accurate, complete, and current information about any aspect of the investigation.

# **Investigators Records and Reporting**

# Records 21 CFR 812.140 (a)(3)(i)

The investigator maintains records of each subject's case history and exposure to the device and supporting data including signed and dated consent forms, health assessment form, and progress notes during the study. Records should show evidence that informed consent was signed and dated prior to the subject participating in the study.

#### Reports 21 CFR 812.150 (a) 1,2,5,7

The investigator shall prepare and submit the following complete, accurate, and timely reports:

Clinimark, LLC	TITLE: BORA Band SpO2 Validation Study	DOCUMENT NUMBER	REV
[name]	Study ID# PR 2018-312	PR# 2018-312	1
[name], USA	Principal Investigator: [name] Site ID # 001	Page 33 of 36	

#### Unanticipated adverse device effects

The investigator shall submit to the sponsor and to the reviewing IRB a report of any unanticipated adverse device effect occurring during an investigation as soon as possible, but in no event later than 10 working days after the investigator first learns of the effect.

#### Withdrawal of IRB approval

The investigator shall report to the sponsor, within 5 working days, a withdrawal of approval by the reviewing IRB of the investigator's part of an investigation.

# **Informed consent**

If an investigator uses a device without obtaining informed consent, the investigator shall report such use to the sponsor and the reviewing IRB within 5 working days after the use occurs.

#### Other

The investigator shall, upon request by a reviewing IRB or FDA, provide accurate, complete, and current information about any aspect of the investigation.

# Withdrawal, Early Termination or Suspension of the Investigation

Participation in the study is voluntary. Subjects may choose to withdraw from the study at any point. If a subject officially withdraws from the study, the laboratory staff will document the reason for withdrawal in the case report.

It is recognized that some subjects may not be able to tolerate the lowest hypoxia levels in a stable manner. These subjects will be moved to higher  $SaO_2$  levels for final data collection if needed. This is not considered to be a withdrawal or discontinuation of the subject and therefore will not be reported as such. These subjects are considered to have completed the study procedure without incidence or any adverse events.

Participation in the study may also be stopped at any time by the principal investigator or by the Sub-investigators or sponsor.

- The subject's failure to cooperate fully (as determined by the investigator in his or her sole discretion) with the required conduct of this study.
- The subject's development of an illness as determined by the investigator in his or her sole discretion.
- A determination by a Clinimark representative (in his or her sole discretion), for whatever cause, that the study should be discontinued.
- A determination by the sponsor (in his or her sole discretion), for whatever cause, that the study should be discontinued

The collection of data for study subjects will cease in the following cases:

- Subject completes all study requirements
- Subject withdraws consent
- Investigator's decision that it is in subject's best interest to be discontinued from the study
- Subject death
- Adverse event other than death requiring withdrawal of the subject from the study
- Determination that the subject was ineligible for the study.

Clinimark, LLC	TITLE: BORA Band SpO2 Validation Study	DOCUMENT NUMBER	REV
[name]	Study ID# PR 2018-312	PR# 2018-312	1
[name], USA	Principal Investigator: [name] Site ID # 001	Page 34 of 36	

There will not be any follow-up procedures for withdrawn or discontinued subjects required, unless a follow-up is required at the Investigator's discretion.

Consideration for early termination or suspension of the investigation is tied to unanticipated equipment failure or a decision by the sponsor or the site. Both BiOSENCY and Clinimark reserve the right to discontinue the study at any time for administrative or other reasons. Written notice of study termination will be submitted to the investigator in advance of such termination. Termination of a specific site can occur because of, but not limited to, inadequate data collection, low subject enrollment, or non-compliance with the protocol or other research requirements.

Early termination results when the study is closed prior to the end of the study. A study suspension is a temporary postponement of the study activities related to enrollment. Both are possible for the study.

If the study is terminated or suspended, no additional enrollment will be allowed unless otherwise informed by the sponsor. The current subjects will be followed according to the protocol.

If the study is terminated prematurely or suspended by the sponsor/investigator, the sponsor /investigator will promptly inform the regulatory authorities (if required) of the termination and the reason(s). IRB/IECs will also be promptly informed and provided with the reason(s) for termination or suspension by the sponsor/investigator. The investigator will promptly inform the subjects and assure appropriate follow-up for the subject.

If the investigator (or IRB/IEC) terminates or suspends the investigation the investigator will promptly inform the institution (if required) and the IRB/IEC to provide a detailed written explanation of the termination or suspension. The investigator will promptly inform the subjects and assure appropriate therapy and follow-up for the subjects. The sponsor will inform the regulatory authorities (if required).

Withdrawal of IRB approval shall be reported to the sponsor by the investigator within 2 working days.

In case of early termination of the study, all study subjects should be followed until the resolution of any pending adverse event(s).

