# **Controlled Desaturation Study**

Desaturation of the subject involves the administration of oxygen/nitrogen mixtures that are less than that of normal air, i.e., less than 21% oxygen. The minimum percentage of oxygen to be delivered is 9% which results in blood oxygen saturation levels similar to those that are seen in healthy individuals who are at a 14,000 to 17,000 feet elevation. Potential symptoms include air hunger, dizziness, faster breathing, higher pulse rate followed by slowing of the heart rate, anxiety, changes in the heart rhythm, sweating, flushing or feelings of being hot and tingling in the hands or feet or loss of consciousness. Vision changes such as 'starring' or 'tunnel vision' can also occur. In the event of any of the above symptoms the subject can be returned to room air or given high levels of oxygen. All of these symptoms, if they occur, reverse within minutes of discontinuation of the testing. During the test, the subject is closely monitored and constant communication regarding the subjects comfort and sense of well-being is assessed. The ECG, pulse oximetry saturation, inspired and expired oxygen, and exhaled carbon dioxide are monitored. Since 1983 Clinimark has performed these types of tests in this and other laboratories where we conducted approximately 10,000 desaturation tests with no significant negative events.

The mask allows gas for maximum delivery. The mask is made of soft flexible plastic so as to minimize the discomfort level as much as is reasonably possible. Materials may cause some skin irritations.

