- 25. The clinician monitors and records the following information periodically. SpO2, pulse rate, EtCO2, respiration rate, relevant information on the ECG rhythm, FiO2. The clinician will monitor the subject's wellbeing throughout the test confirming that the subject is doing ok.
- Subject will be advised during the study that he/she may stop the test at any time.
- 27. The gas controller monitors the gas delivery and data collection system to ensure proper functionality. Performance of the test devices may be noted on the form as well.
  - The test may be stopped at any time by the subject, the clinician, the gas controller. The test will also be stopped if the SpO2 level goes below the minimum SpO2 or the FiO2 goes below 9%.
- 28. Arterial blood sampling will be repeated at each stable plateau. Method used will be same as described in step #22 above.

Goal is to collect 20-30 data points per subject with an equal distribution of data by decade across all subjects. The stable plateaus will allow for data to be collected in the following ranges 95-100, 90-95, 85-90, 80-85, 75-80, 67-75. In general, 4 to 8 discrete points will be collected at each of the levels such that the overall data of the population is evenly distributed by decade and the minimum number of points is met for the data analysis. A fewer number of data points are expected on some subjects that are unable to tolerate the duration of the lower hypoxic levels.

- 29. During the course of the study, the subject may be re-saturated to above 80% SpO2 for a recovery period. The subject then may reattempt the lower SpO2 levels.
- 30. Once the lowest level SpO2 has been achieved and data collection has been completed, the subject will be given a gas mixture returning him/her to baseline levels.
- 31. The breathing circuit is disconnected and the subject is monitored for a few minutes to ensure he/she maintains normal baseline levels.
- 32. All equipment will be removed from the subject.
- 33. The arterial line will be removed and a pressure bandage will be applied to the subject for approximately 15 minutes or until bleeding has stopped.

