## **Adverse Event Definitions**

The definitions for adverse event, adverse device effect, serious adverse event, serious adverse device effect, unanticipated adverse device effect, and their classifications are provided below (ISO 14155, 21 CFR 812.3).

- Adverse Device Effect (ADE): Adverse event related to the use of an investigational medical
  device resulting from insufficiencies or inadequacies in the instructions for use, the
  deployment, installation, the operation, or any malfunction of the investigational medical
  device or from error use.
- Adverse Event (AE): Any untoward medical occurrence, unintended disease or injury or any
  untoward clinical signs (including an abnormal laboratory finding) in subjects, users or other
  persons whether or not related to the investigational medical device or investigational
  procedure
- Anticipated Serious Adverse Device Effects (ASADE): ASADE is an effect which by its nature, incidence, severity or outcome has been identified in the risk analysis report.
- **Mild:** a mild adverse event is one in which the subject is aware of the event, but it is easily tolerated without intervention.
- Moderate: a moderate adverse event is one that causes sufficient discomfort to interfere
  with usual activities.
- Serious Adverse Device Effect (SADE): adverse device effect that has resulted in any of the consequences characteristic of a serious adverse event
- Serious Adverse Event (SAE): a serious adverse event is an adverse event that results in
  death, inpatient hospitalization, severe or permanent disability, a life threatening illness or
  injury, fetal distress, fetal death, a congenital abnormality, a birth defect, or medical or
  surgical intervention to prevent permanent impairment to body or structure.
- Severe: a severe adverse event is one that results in the inability to perform usual activities.
- Unanticipated Adverse Device Effect (UADE): serious adverse device effect which by its
  nature, incidence, severity or outcome has not been identified in the current version of the
  risk analysis report.

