# **Management of Adverse Event Reporting**

Should the subject experience an adverse or non-typical event, assessment of the situation is first initiated, and a determination will be made of appropriate actions. The Medical Director and Principle

Clinimark, LLC	TITLE: BORA Band SpO2 Validation Study	DOCUMENT NUMBER	REV
[name]	Study ID# PR 2018-312	PR# 2018-312	1 1
[name], USA	Principal Investigator: [name] Site ID # 001	Page 31 of 36	1

Investigator will be contacted as appropriate. Adverse Events are reported through standard Clinimark Procedures, IRB requirements and per BiOSENCY's SOPs.

Records of Adverse events will be recorded in the Case Report Form The following information will be obtained:

- Type of effect (ADE, AE, ASADE, SADE, SAE, UADE)
- Date of onset and resolution
- Intensity (mild, moderate, severe)
- Serious (yes/no)
- Relationship to device (unknown, not related, possibly related, probably related, definitely related)
- Anticipated (yes/no)
- Treatment given and / or action taken (procedure stopped, withdrawn from study, no action)

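### Subjects moved off the lowest hypoxia levels and kept in the study are deemed free of adverse events, whether or not they had symptoms

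*Combined protocol and SAP*

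**What the plan says.** The rule is in the protocol section Withdrawal, Early Termination or Suspension of the Investigation. It concerns subjects who cannot hold the lowest hypoxia levels stably and who are moved to higher SaO2 levels for their remaining data if needed. Two statements follow:

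- On the move: "This is not considered to be a withdrawal or discontinuation of the subject and therefore will not be reported as such".
- On the subjects: "These subjects are considered to have completed the study procedure without incidence or any adverse events".

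The plan expects such subjects. Procedure, step 28, says: "A fewer number of data points are expected on some subjects that are unable to tolerate the duration of the lower hypoxic levels". Step 29 makes re-saturation a permitted part of the session.

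The general safety rules are elsewhere. Adverse Event Definitions opens its definition of an AE with "Any untoward medical occurrence, unintended disease or injury or any" and extends it to untoward clinical signs in "persons whether or not related to the investigational medical device or investigational" procedure. An event that is easily tolerated still counts, as mild. Management of Adverse Event Reporting calls for an assessment when an adverse or non-typical event occurs and for AEs to be entered in the CRF. One of the recorded attributes is whether the event was anticipated.

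Controlled Desaturation Study describes what low oxygen may do: "Potential symptoms include air hunger, dizziness, faster breathing, higher pulse rate followed by slowing of the heart rate, anxiety", with visual changes and others also listed. It adds: "In the event of any of the above symptoms the subject can be returned to room air or given high levels of oxygen".

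**The concern.** The first statement about these subjects settles their completion status, and that is reasonable because moving up is a planned step. The second goes further and assigns their AE status in advance, as a group. Whether a subject had an AE should depend on what happened to that subject. Having been moved to a higher level does not answer the question.

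A symptom during desaturation is a plausible reason for the move, so the blanket rule applies where AEs are most likely to need assessment. At stake is the completeness of the safety record in a study that gives healthy volunteers an arterial line and induced hypoxia. The accuracy claim is not at stake.

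**Working it through.** No arithmetic applies. The check is to apply both rules to each kind of subject the plan allows for.

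1. **Unstable plateau, no symptoms, moved up.** The AE definition gives no event, and neither does the withdrawal section. The rules agree.
2. **Symptom such as dizziness, anxiety or visual change; moved up; continues.** Under Adverse Event Definitions and Management of Adverse Event Reporting, the occurrence is assessed and, if judged untoward, recorded even if mild. Under the withdrawal section the subject is already classed as having had no AE. The rules disagree.
3. **Arrhythmia (other than sinus arrhythmia below 120 bpm), clinically significant ST or T changes, sustained sinus tachycardia of 120 bpm or more, or onset of PVCs.** Criteria for Study Termination ends the session. The subject does not continue, so the disputed sentence does not apply.
4. **AE requiring withdrawal.** The termination criteria include stopping for an AE, and the withdrawal section lists an AE requiring withdrawal as a separate reason to cease data collection. The disputed sentence does not apply.

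The conflict is therefore confined to case 2.

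Next, does another provision decide case 2?

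- Procedure, step 34, has the clinician ask about effects at the end. This can bring a symptom to light but does not classify it.
- The Monitoring Plan verifies that AEs are documented and reported. It does not say whether this symptom is one.
- Data Collection Forms / Case Report Forms requires a Sub-Investigator or Investigator to sign AE reporting along with the designee, but lists that reporting as needed only where applicable. The disputed sentence gives staff a reason to decide that it is not.
- Deviations from the Clinical Investigation Plan bars departures outside emergencies. Staff who follow either rule can say that they followed the plan.

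None of these limits the sentence for subjects who are moved up and continue.

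Finally, the accuracy result. In Statistical Analysis, pairs are removed for control-oximeter instability, CO-oximetry anomalies, SaO2 below 67%, truncated or zero test readings, or low perfusion. AE status is not among these criteria and does not enter the A_RMS formula or the 3.5 limit. Reclassifying a subject's AE changes none of them.

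**The case against.** The best case for the plan has four parts.

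- **Context.** The paragraph is about completion and withdrawal. Read there, its last sentence most naturally means that the move is not in itself an incident. The most literal reading would also erase an arterial-line hematoma in such a subject, which the plan can hardly intend given its other AE provisions. This stands as an account of intent, but the text speaks of the subjects and of any AE. The wording should say what was meant.
- **Clinical judgement.** The AE definition requires an untoward occurrence. Whether brief air hunger during deliberate hypoxia is untoward is for the clinician, and the reference to non-typical events leaves room to treat typical effects differently. The anticipated yes/no field does not make every expected symptom an AE. This also stands, and it means that not every symptom would be recorded. It does not justify deciding the question in advance for a whole group.
- **Serious cases go elsewhere.** This stands largely as shown in cases 3 and 4. Controlled Desaturation Study says that the symptoms reverse within minutes, so mainly mild, transient events remain.
- **Unseen procedures.** AE reporting also follows site procedures, IRB requirements and sponsor SOPs, including a named AE reporting document that is not reproduced. It may settle the classification. This cannot be excluded, so the finding is limited to the protocol text.

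A reader might infer that the plan sets out to keep AEs out of the report, or that serious cardiac events could be hidden by this route. The documents support neither: enquiry, monitoring, signature and termination rules all remain in force.

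**Conclusion.** The point holds in limited form. For a subject who has a symptom, is moved up and continues, the protocol contains two AE rules that can give different answers. The literal effect of one is that an AE may go unrecorded. This should be corrected, but it is a wording conflict in safety reporting and not a flaw in the design.

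The conclusion assumes that a symptom can be the reason for a move, which Controlled Desaturation Study supports, and that at least some such symptoms would be judged untoward.

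No size can be given. The plan says only that some subjects will be affected. It states no intolerance rate or AE rate, and its statistical section plans no AE proportion and sets no safety threshold. If staff already apply the AE definitions to these subjects, the effect is zero. A reader might infer a quantifiable bias in the safety results or a threat to the accuracy claim; the documents give no basis for the first and rule out the second. Follow-up contact for withdrawn subjects is a separate matter, since the subjects discussed here are not counted as withdrawn.

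**What to change.** In Withdrawal, Early Termination or Suspension of the Investigation, replace the last sentence of the paragraph on intolerance with:

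> Inability to tolerate the lowest level, or a move to a higher SaO2 level, is not in itself a withdrawal or an adverse event; any associated symptoms or signs are assessed under the Adverse Event Definitions and recorded in the CRF.

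This keeps the likely intent and leaves one AE rule for every subject. It changes no hypoxia procedure, sample size or accuracy analysis. As a protocol amendment it needs sponsor and IRB approval. The downside is that the reported AE count may rise slightly.

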  - history of bleeding disorders or personal history of prolonged bleeding from injury
  - history of blood clots
  - o hemophilia
  - current use of blood thinner: prescription or daily use of aspirin
- Subjects with severe contact allergies to standard adhesives, latex or other materials found in pulse oximetry sensors, ECG electrodes, respiration monitor electrodes or other medical sensors (self-reported)
- Subjects with severe allergies to iodine (only applicable if iodine is used)
- Subjects with severe allergies to lidocaine (or similar pharmacological agents, e.g. Novocaine)
- Failure of the Perfusion Index Ulnar/Ulnar+Radial Ratio test (Ratio < 0.4)
- Unwillingness or inability to remove colored nail polish from test digits.

Clinimark, LLC	TITLE: BORA Band SpO2 Validation Study	DOCUMENT NUMBER	REV
[name]	Study ID# PR 2018-312	PR# 2018-312	1
[name], USA	Principal Investigator: [name] Site ID # 001	Page 5 of 36	

- Other known health condition, should be considered upon disclosure in health assessment form
- Wrist size should be between 15-23 cm (5.9 9 inches)

Data collection will occur over a 3-5 day period for this study population. Follow-up with each subject will be conducted within 5 days following participation in the study and will be conducted via telephone, text or email.

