# **Criteria for Study Termination**

The study will be terminated if any of the following conditions occurs:

- Study is complete
- Unable to obtain vascular access
- Initial blood draw values of, COHb >3%, MetHb > 2%, and tHb <10g/dl (Note: COHb may be lowered through an exercise of hyperventilation and elevated levels of oxygen being administered to the subject.)
- Subject withdrew consent. The subject may stop the study for any reason without prejudice
- Withdrawal by Sub-Investigator / Investigator. The clinician or gas controller may terminate the study at his/her discretion
- Study Stopped due to Technical Problems
- Study may be stopped due to Protocol Deviation
- Study Terminated by Sponsor
- Study Stopped due to Adverse Event
- Development of any cardiac arrhythmia, except sinus arrhythmia <120 bpm
- Development of clinically significant ST or T segment changes in the ECG

Clinimark, LLC	TITLE: BORA Band SpO2 Validation Study	DOCUMENT NUMBER	REV
[name]	Study ID# PR 2018-312	PR# 2018-312	1
[name], USA	Principal Investigator: [name] Site ID # 001	Page 19 of 36	1

- Sustained sinus tachycardia ≥120 bpm
- Onset of PVCs
- Sustained levels lower than the target SpO2. The lowest target is 70% SpO2. Due to unpredictable human physiology, the subject may drift below 67%. Should this occur, an attempt will be made to increase the oxygen saturation level by increasing the FiO2 level to achieve an SpO2 in the 67-73% range or a decision is made to increase the FiO2 to a new SpO2 range or terminate the study.

Any data collected to the point of a decision to terminate the study will be reviewed for inclusion to the analysis prior to generation of the final results. Data excluded from the analysis will be documented with justifications.

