# **Procedure**

- 1. Complete Equipment checkout list prior to starting study. Calibrate / check FiO2 monitor(s).
- Set the clocks to sync data collection between the Sponsor and Clinimark systems.
- 3. Explain the procedure to the subject. Have them read the Informed Consent Form, and review the information answering all questions. Once all questions have been answered, have the subject sign the form. Have the subject complete the Health Assessment Form and verbally question the subject about their health history. Each subject will be asked if they want a copy of the consent form prior to release.
- 4. Apply Finger sensor to thumb of hand where the arterial line will be placed. Record perfusion index (PI) value from 3900 TT+ Pulse Oximeter. Perform a modified Allen's test to ensure sufficient blood flow to the hands. Occlude both radial and ulnar arteries until there is no plethysmographic waveform and the PI is essentially zero. Release the ulnar artery holding the radial artery firm. Record the PI level. The ratio of the ulnar artery PI measurement to the starting PI level should be greater than or equal to 0.4 to qualify for the study. This is a safeguard to ensure there is a sufficient blood flow supply to the hand should the flow from the radial artery become altered.
- 5. Take subject's blood pressure and record values.
- 6. Apply ECG leads to the subject, review for normal sinus rhythm.
- 7. Based on the responses to the Health assessment form, record accepted or declined from the study. Continue if accepted into the study.
- 8. A qualified clinician will use local anesthesia and with the assistance of ultrasound, place the arterial catheter in the radial artery of the non-dominate (preferred) hand. The arterial line is then secured with tape to the subject's arm.
- 9. Setup and verify communication between the devices and data collection system.
- 10. Record device information for tracking. (manufacturer, model #, serial or lot, hardware / software control info).
- 11. Record subject information. Subject number and demographics information for subject description.
- 12. Have subjects recline.
- 13. Apply sensors to the subject. Shield any adjacent sensors to prevent optical cross-talk.
- 14. Adjust sensors as appropriate and record on test form.
- 15. A hot water bottle may be placed on each arm to improve the perfusion and facilitate the blood draws.

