- 16. Allow readings to stabilize. Record baseline SpO2 and Pulse rate on the test form.

Clinimark, LLC	TITLE: BORA Band SpO2 Validation Study	DOCUMENT NUMBER	REV
[name]	Study ID# PR 2018-312	PR# 2018-312	1
[name], USA	Principal Investigator: [name] Site ID # 001	Page 20 of 36	

[figure not shown]

- 17. Begin program to start gas flow. Verify that FiO2 is at appropriate starting level (typically 18-21%) prior to connecting subject to breathing circuit.
- 18. Connect the subject to the breathing circuit and adjust the gas flow delivery for subject comfort.
- 19. Start data collection.
- 20. The program will be run in manual mode. Gas mixture changes will be set by the controller. The gas mixture will be delivered to induce hypoxia in a stair stepped manner. Data collection will be evenly distributed by decade over the oxygen saturation range.
- 21. The clinician monitors and records the following information periodically. SpO2, pulse rate, EtCO2, respiration rate, relevant information on the ECG rhythm, FiO2. The clinician will monitor the arterial line and subject's well-being throughout the test confirming that the subject is doing "ok". Subject will be advised during the study that he/she may stop the test at any time.
- 22. While breathing room air mixtures, collect baseline arterial samples and measure on the CO-Oximeter. The method for sampling will be:
  - Mark data for start of stability period hold 30 seconds to 1 minute
  - Draw waste or leader blood sample prior to draw, mark data
  - Draw arterial blood sample marking data
  - Wait approximately 15 to 30 seconds, draw waste or leader blood sample prior to draw
  - Draw additional arterial blood sample marking data
  - · Change to next gas level

Note timing may vary based on the subject's stability.

- 23. Should the initial COHb reading be out of range (>3%) as measured by Reference CO-Oximetry, then a determination will be made as to the viability of blowing off the COHb levels through an exercise of hyperventilation and elevated levels of oxygen being administered to the subject. If this is the case, blood samples will be drawn to monitor the COHb level until it is acceptable or a determination is made to withdraw the subject.
- 24. Multiple plateaus will be achieved throughout the range from 100% to 70%.

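### The plan does not say whether the 5-day contact covers subjects withdrawn after arterial puncture or because of an adverse event

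*Combined protocol and SAP*

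**What the plan says.** Two provisions of the combined protocol and SAP deal with contact after the session.

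- Synopsis, closing paragraph under Exclusion Criteria: "Follow-up with each subject will be conducted within 5 days following participation in the study". The contact is by telephone, text or email. No exception is made, and the purpose of the contact is not stated. The body of the protocol does not repeat the timing.
- Withdrawal, Early Termination or Suspension of the Investigation: "There will not be any follow-up procedures for withdrawn or discontinued subjects required, unless a follow-up is required at the Investigator's discretion". The same section lists when data collection on a subject ceases, and that list includes "Adverse event other than death requiring withdrawal of the subject from the study". The waiver makes no exception for such a subject, nor for one who has had an arterial puncture.

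The same section also requires pending adverse events to be followed to resolution if the study terminates early. It defines early termination as closure of the study before its end.

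Arterial access comes early in the session. At Procedure step 8 a clinician is to "place the arterial catheter in the radial artery of the non-dominate (preferred) hand". The first blood draw is at step 22. Criteria for Study Termination then gives two stopping reasons tied to arterial access: "Unable to obtain vascular access" and "Initial blood draw values of, COHb >3%, MetHb > 2%, and tHb <10g/dl". When the initial COHb is high, step 23 says that "blood samples will be drawn to monitor the COHb level until it is acceptable or a determination is made to withdraw the subject".

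**The concern.** The Synopsis rule covers everyone, and the withdrawal rule removes the obligation for one group. A site working from the body of the protocol finds the waiver but not the 5-day timing.

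That group can include people for whom a later check is useful. The Radial Arterial Line section lists hematoma and clotting among the catheter risks. If a subject leaves early after cannulation and nobody makes contact, an event after release may not be asked about. The order also looks odd: an uneventful completer is assured a contact, while a subject withdrawn because of an adverse event may have follow-up only if the investigator asks for it. What is at stake is complete safety ascertainment in a small invasive study of healthy volunteers, not device accuracy.

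**Working it through.** The only figure involved is the 5-day window, and it is as the Synopsis states it. The check is a comparison of rules.

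**1. What each rule gives each type of subject.**

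| Subject | If the Synopsis rule prevails | If the withdrawal rule prevails |
|---|---|---|
| Completes the session | Contact within 5 days | Contact within 5 days |
| Cannot tolerate the lowest hypoxia levels (expressly not counted as withdrawn) | Contact within 5 days | Contact within 5 days |
| Withdrawn after arterial puncture or an attempt | Contact within 5 days | Investigator's discretion |
| Withdrawn because of an adverse event | Contact within 5 days | Investigator's discretion |
| Withdrawn before any arterial attempt | Contact within 5 days | Investigator's discretion |

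The rules differ in the last three rows. The plan does not say which column applies.

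**2. Can a subject be withdrawn after arterial access?** Yes. Cannulation is at step 8, the subject joins the breathing circuit at step 18, and the first samples are drawn at step 22. Step 23 expressly foresees withdrawal on the COHb result. Consent may be withdrawn at any time. Withdrawal for an adverse event is listed in the withdrawal section itself.

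**3. Does another provision settle it?**

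- *Follow-up of pending adverse events on early termination.* As defined, this concerns closure of the whole study. Even on a looser reading it covers only events already open and sets no contact to detect new ones.
- *Procedure step 34.* The subject is asked about effects, receives wrist-care instructions and phone numbers, and is told of the follow-up procedure. No timing is given there, and a later call is left to the subject.
- *The follow-up form in the case report forms, and the monitor's check that these forms are complete.* Neither states that the form applies to a subject for whom follow-up is not required.
- *Adverse event records.* These include a resolution date, and withdrawal is one of the listed actions. That helps for events already known at release but not for new ones.

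These controls reduce the gap. None says that a withdrawn subject will be contacted.

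**4. Size.** No withdrawal rate is given, so no expected number can be derived. The workload has a ceiling: with 10 to 15 subjects and one contact each, at most 15 × 1 = 15. If the Synopsis rule already governs, the fix adds 0 contacts. If the withdrawal rule governs, it adds at most one per withdrawn subject who had an arterial line or an attempt.

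**The case against.** The strongest reply is that the gap exists on only one reading. The Synopsis is unqualified. The waiver follows a list of when data collection stops, so it could mean that no further study procedures are needed and leave the short contact in place. This is a fair reading, and it limits the point. A reader might infer that withdrawn subjects definitely have no scheduled contact. The documents do not support that, because they do not say which rule prevails. They support only that the contact is not assured.

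Second, the plan uses study termination for single-subject stops, and does not say that everyone so stopped counts as withdrawn or discontinued. Failed vascular access is not in the withdrawal section's list, and step 23 speaks of withdrawal for COHb only. This stands as a caution against counting stopping reasons. It does not remove the routes that are expressly withdrawals: consent, COHb at step 23, and an adverse event requiring withdrawal.

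Third, late harm is inferred. The catheter risks are listed without onset times and the overall risk is called minimal. Step 33 applies pressure for about 15 minutes or until bleeding stops. A reader might also infer delayed harm from hypoxia, but the protocol says those symptoms reverse within minutes, and step 31 monitors the subject afterwards. All of this stands, and it is why the point is minor.

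Finally, the consent form and wrist-care instructions are separate documents that were not available. They may settle the matter.

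**Conclusion.** The two follow-up rules conflict as written, and the plan does not resolve the conflict. A subject withdrawn after arterial puncture or an attempt, or because of an adverse event, is not assured the 5-day contact. This is a minor safety-ascertainment inconsistency and a cheap one to repair. Its frequency is unknown. It has no bearing on A_RMS, the sample size or the pass/fail decision. The conclusion rests on the protocol text alone and assumes that the unseen subject documents do not already guarantee the contact.

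**What to change.** Replace the last sentence on withdrawn and discontinued subjects with wording to this effect: *Every subject who had arterial line placement or an attempt, including one who withdraws or is discontinued, will be contacted by telephone, text or email within 5 days of participation unless the subject refuses; any adverse event pending when the subject is stopped is followed to resolution; any other follow-up is at the Investigator's discretion.* This also puts the 5-day timing into the body of the protocol.

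Amend the Synopsis sentence to match. It should either include subjects stopped before any arterial attempt or expressly except them; otherwise the conflict remains for that group.

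The burden is at most one brief contact per withdrawn subject, none of it beyond what the Synopsis already promises, plus follow-up of any open adverse event. The change needs an amendment approved by the sponsor and then the IRB.
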